This will be a randomized clinical trial. Subjects will be randomly allocated to each group. There will be roughly equal number of subjects in each arm. Arm 1 will be patients receiving sclerotherapy and ablation at the start of treatment along with compression therapy. The patients in arm 1 will not receive any further treatment during the duration of the study. Arm 2 will be patients who receive sclerotherapy at the start of treatment along with compression therapy, and ablation 3 months later. All patients in arm 2 will receive ablation at their 3 month appointment. After ablation, the patients in arm 2 will not receive any further treatment for the remainder of the study.

30 opaque envelopes, 15 indicating arm 1 and 15 indicating arm 2, will be prepared by the study coordinator. Patients who agree to participate will select an envelope and treatment will be initiated based off of the arm that is selected. In the event of a participants early termination from the study, up to 5 study participants will be replaced in each study arm to help ensure an adequate number of subjects for analysis. The purpose of this study is to see if one treatment is more effective over the other in treating chronic venous ulcers.

Patients who participate will have ultrasound-guided sclerosant injected into the affected area. Half of the patients will only receive injections (arm 2) while the other half of the patients will receive injections along with ablation (arm 1). Patients in arm 1 will not receive any further

treatment during the remainder of the study. All patients will fill out a quality of life questionnaire (using the VEINES-QOL/Sym questionnaire) and complete the venous clinical severity score (VCSS) questionnaire prior to treatment. All patients will undergo compression therapy.

Patients will be seen weekly after treatment. Safety assessments will take place during these weekly appointments to ensure patient safety. After 3 months, patients will be brought in for another follow up visit. The 3 month follow up is considered standard protocol after these procedures to monitor for adverse events. Ulcer size, symptoms, healing rate, quality of life (using the VEINES-QOL/Sym questionnaire), and venous clinical severity score (VCSS) will be assessed. All patients in arm 2, will receive ablation at this time.

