All patients will continue to be seen weekly to assess healing progress and to ensure patient safety. Six months following initial treatment, the patients will return for another follow up visit where ulcer size, symptoms, healing rate, quality of life (using the VEINES-QOL/Sym questionnaire), and VCSS will be assessed. Participation in the study will be complete after the 6 month follow up appointment. Patients will continue to see their physician for treatment, if needed, after their participation has concluded.

All treatments and appointments are considered standard of care and will be billed to the patients insurance.

Following completion of data collection (see study variables on attached excel sheet), analysis will be completed to identify study results. We will be analyzing the differences between the two groups in A. ulcer healing rate (comparison of means, generalized linear model), and B. proportion of healed ulcers (Chi square).

Inclusion/Exclusion Criteria

Inclusion Criteria:

- Patients 18 years of age and older
- Patients who have saphenous vein reflux and a single venous ulcer of any size

Exclusion Criteria:

- Patients under 18 years of age
- Patients with multiple venous ulcers

How Human Subjects will be involved

All enrolled subjects will have ultrasound-guided sclerosant injected into the affected area. At the start of treatment, half of the patients will receive injections at the start of treatment and ablation 3 months later (arm 2) while the other half of the patients will receive injections in addition to ablation at the start of treatment (arm 1). All patients will undergo compression therapy following treatment.

Risks/Side-effects

During the **sclerosant injections**, some people experience minor stinging or cramps when the needle is inserted into the vein. The risks associated with the injection include, but are not limited to, bruising, raised red areas, small skin sores, darkened skin in the form of lines or spots, and multiple tiny red blood vessels. These side effects usually go away within a few days to several weeks. Other more serious side effects include, but are not limited to, inflammation, blood clot, air bubbles and allergic reaction.

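### Treatment rules without exception, and safety visits with no stated consequence, leave early termination with replacement as the only visible exit and conflict with Aim 4

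*Combined protocol and SAP*

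**What the plan says.** The treatment sequence is set out in Methods of the combined protocol and SAP.

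- Arm 1: "The patients in arm 1 will not receive any further treatment during the duration of the study". The same bar is repeated later in the section.
- Arm 2: "All patients in arm 2 will receive ablation at their 3 month appointment". The description of the month 3 visit lists the assessments and then repeats the rule: "All patients in arm 2, will receive ablation at this time". Afterwards: "After ablation, the patients in arm 2 will not receive any further treatment for the remainder of the study". Additional treatment in arm 2 between baseline and month 3 is not addressed.

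None of these sentences carries an exception.

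On monitoring, Methods says: "Safety assessments will take place during these weekly appointments to ensure patient safety". It describes the month 3 visit as the usual check for adverse events. For months 3 to 6 it says: "All patients will continue to be seen weekly to assess healing progress and to ensure patient safety". No threshold, decision rule or discontinuation criterion is attached to any of these visits.

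Methods mentions treatment by the patient's own physician, where required, only for the time after participation has ended. Methods and Number of Subjects both foresee early termination, with up to 5 replacements per arm, and give no criteria for it. Efficacy aim 4 under Specific Aims compares the arms on ulcer outcome and on the need for retreatment. The analysis paragraph names a comparison of mean healing rates (generalized linear model) and a chi-square test of the proportion healed. It does not say how deviations, retreated patients or replaced patients are handled.

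**The concern.** A protocol that schedules safety visits throughout should say what a finding at one of them can lead to. Here the treatment sentences leave no room for a change on study, and the visit sentences propose none. The patient's position is therefore undefined.

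For the statistician the main issue is who remains in the data. If treatment outside the sequence is possible only after participation ends, the patients most likely to stop early are those whose ulcers are not healing or who have complications. Those reasons are tied to the outcome. Replacing such patients substitutes new ones for those who were doing badly, and both planned comparisons, healing rate and proportion healed, are exposed to this. Separately, Aim 4 asks for a comparison that the treatment rules largely prevent from being observed.

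**Working it through.** The plan gives no event rates, power calculation or figure for this point. The main check is to set the passages side by side.

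**1. Rules by period (Methods)**

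| Period | Arm 1 | Arm 2 | Action tied to a visit finding |
|---|---|---|---|
| After initial treatment, to month 3 | further treatment barred | not addressed | none stated |
| Month 3 visit | further treatment barred | ablation for all | none stated |
| Month 3 to month 6 | further treatment barred | barred after ablation | none stated |
| After participation | own physician, if required | own physician, if required | not applicable |

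The bar runs for 6 months in arm 1 and for 3 months in arm 2. Any pressure to leave the study need not be equal in the two arms.

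**2. Route out.** Early termination followed by treatment from the patient's physician is the only path the text shows. It takes the patient out of the study.

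**3. Scale of replacement.** Inputs from Methods and Number of Subjects: target 15 per arm, up to 5 replacements per arm. 2 × (15 + 5) = 40, which agrees with the stated maximum of 40 subjects. 5 / 15 = one third of an arm's target.

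**4. Illustration of the bias (assumptions mine).** Let h be the proportion of an arm's 15 patients who would be healed at month 6 if all were followed. Suppose k patients leave, none of whom would have healed. They are replaced by k patients who heal at rate h and do not leave, and only the resulting 15 are analysed.

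Observed proportion healed = (15h + kh) / 15 = h(1 + k/15).

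- h = 0.5, k = 0: 0.50.
- h = 0.5, k = 5: 0.5 × (1 + 5/15) = 0.667, a shift of about 17 percentage points.
- Largest shift with at most 5 replacements: h = 2/3, where all 5 unhealed patients leave. 2/3 × 5/15 = 0.222, about 22 points.
- If leaving is unrelated to healing, the expected shift is 0.

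The value h = 0.5 is a convenience. Background says more than half of these ulcers are unhealed after 9 months. If that applied here, at least 0.5 × 15 = 7.5, or about 8 per arm, would be unhealed at month 6. Background also says that healing after sclerotherapy usually comes within 4 to 8 weeks. If that applied, few would be unhealed and few would have this reason to leave. The between-arm difference is biased only so far as the shift differs between arms.

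**5. Aim 4 against the bar.** If the rules are followed, retreatment received is zero in arm 1 for the whole study and zero in arm 2 after ablation. Any retreatment in those periods is a protocol deviation. The one period without a bar, arm 2 up to month 3, has no counterpart in arm 1. The need for retreatment, as distinct from its receipt, is not defined.

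**The case against.** Several stronger readings are tempting, and the documents do not support them.

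- A reader might infer that the fixed rules contradict the weekly safety visits. Assessment and a fixed sequence can coexist. What is missing is the link from a finding to an action.
- A reader might set the rules against this sentence: "All treatments and appointments are considered standard of care and will be billed to the patients insurance". It classifies and bills the treatments. It makes no promise of individualised treatment.
- A reader might conclude that a patient in trouble cannot be treated at all. Early termination followed by treatment from the patient's physician is a route, so that conclusion fails. The narrower statement stands: no route is given while the patient stays on study.
- A reader might take the bar to exclude compression. The arm definitions include compression, and the protocol later places it after treatment, so further treatment naturally means anything beyond that package.
- Risks/Side-effects says of the injections: "Other more serious side effects include, but are not limited to, inflammation, blood clot, air bubbles and allergic reaction". A reader might infer that mandatory ablation after a clot is a demonstrated harm. The documents do not say whether a clot bears on ablation, and that is a clinical question outside them.
- A reader might suppose that treatment changes would go unrecorded. Methods refers to an attached sheet of study variables that is not available here and may capture them.

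The best defence of the plan is that a fixed sequence protects the contrast in a trial of ablation timing with 15 patients per arm. That is a fair reason to plan a uniform sequence. It does not justify leaving departures, early termination and replacement undefined, or stating an aim on retreatment that the same section bars.

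**Conclusion.** The point holds as a gap in the plan with one clear internal conflict, and it should be corrected. All 30 to 40 patients fall under rules stated without exception, no safety finding has a stated on-study consequence, and the only visible exit can lead to replacement of up to one third of an arm's target. The conflict is between Aim 4 and the bar on further treatment.

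The number of patients affected cannot be estimated. The illustrated shift in an arm's proportion healed runs from 0 to about 17 points at h = 0.5, and to about 22 points at most. It rests on leavers being unhealed, on replacements healing at the arm's rate, and on leavers being dropped from the analysis; the documents do not say whether they would be. The verdict takes the treatment sentences as written and assumes no other document supplies the missing link.

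**What to change.** 1. The sponsor and investigators should reconcile Specific Aims and Methods, stating whether and how findings at the safety visits bear on the planned sequence in each arm, including arm 2 between baseline and month 3. The clinical rule is theirs to set.
2. Make Aim 4 measurable under whatever rule they state. Define need for retreatment, say over which period it is counted in each arm, and say whether it means need or receipt.
3. Record each departure from the planned sequence with its date, the reason and what was given.
4. Keep a patient whose treatment departs from the sequence in follow-up to month 6 and analyse that patient in the assigned arm. Do not treat the departure as early termination or replace the patient.
5. Report departures by arm, and state in the analysis paragraph how they and any replaced patients are handled.

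The cost is a wording amendment and one form, with no added visits or patients. The downside is small: departures kept in the assigned arm may slightly dilute the contrast between arms.

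### One question about which arm works better, but two co-equal healing outcomes, no named visit and no deciding test: the false-claim rate can exceed 5%, and a split result has no stated conclusion

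*Combined protocol and SAP*

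**What the plan says.** Methods states one aim for the trial: "The purpose of this study is to see if one treatment is more effective over the other in treating chronic venous ulcers".

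The analysis paragraph at the end of Methods is the whole statistical plan. It lists two between-arm comparisons: A, "ulcer healing rate (comparison of means, generalized linear model), and B. proportion of healed ulcers (Chi square"). Neither is called primary and no visit is attached to either.

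The data for both are collected twice. At the 3-month visit, "Ulcer size, symptoms, healing rate, quality of life (using the VEINES-QOL/Sym questionnaire), and venous clinical severity score (VCSS) will be assessed". The same measures are repeated later: "Six months following initial treatment, the patients will return for another follow up visit where ulcer size, symptoms, healing rate". Arm 2 has had no ablation before the 3-month visit, receives it at that visit, and so has had it by month 6.

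The documents contain no significance level, sidedness, order of testing, correction for multiple tests, or rule for results that disagree. An attached spreadsheet is mentioned but was not among the documents. The text describes it as holding study variables, not decision rules.

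**The concern.** Two outcomes, each available at two visits, bear on one yes-or-no question, and nothing ties the answer to any one of them. If success on any of them is allowed to count, the claim that one arm is better no longer carries the error rate of a single test. The Dissemination section expects significant findings to be the ones submitted for publication, so selection by p-value is a practical risk.

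A second problem needs no arithmetic. Many ulcers may shrink quickly while few close, or the reverse. The plan then has one significant and one non-significant result and no stated conclusion.

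The rest of the protocol does not settle the visit. The Research Question contrasts sclerotherapy alone with the combination, which only the 3-month comparison can address. The first efficacy aim contrasts immediate with delayed ablation, which points to month 6. Choosing the visit therefore also chooses the treatment comparison.

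**Working it through.** **No figure to reproduce.** The documents give no alpha, power, effect size or expected healing rate, and 15 per arm is stated without derivation.

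**Inputs from the documents.** 15 per arm (Number of Subjects); outcomes A and B with chi-square for B (analysis paragraph); visits at 3 and 6 months (Methods).

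**Assumptions.** Two-sided 5% per test; no true difference between arms; the claim is made if any eligible test gives p ≤ 0.05; a t-test for A.

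**Simulation from healing times.** 40,000 null trials of 15 v 15. Healing times are exponential with log-normal frailty (SD 0.5) and medians of 6, 13, 26 and 39 weeks. Ulcers close linearly from log-normal starting areas. A is percent or absolute area reduction per week up to week 13 or week 26. B is closed or not at that week. Ranges run over the four medians and both definitions of A.

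| Claim made if significant on | Uncorrected chi-square for B | Fisher's test for B |
|---|---|---|
| A or B at month 3 | about 7–9% | about 5–6% |
| A or B at month 6 | about 2–9% | about 1–6% |
| A or B at either visit | about 8–13% | about 5–8% |

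The low month-6 values come from the 6-week median. Ignoring frailty, the share closed by week 26 is then 1 − 0.5^(26/6) = 95%, so few trials can show any difference. At the other three medians the month-6 rate with uncorrected chi-square is 7.2–9.4%. Fisher's figures are lower because its own rate in samples this small is below 2%.

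**Second model, as a check.** Correlated normal variables, about 40% healed at month 3 and 57–65% at month 6, correlation 0.5–0.9 between visits and 0.5–0.95 between outcomes:

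- A or B at month 6: 7.9–9.7% uncorrected, 5.5–6.3% with continuity correction.
- A or B at either visit: 11.7–16.4% uncorrected, 8.1–11.3% with continuity correction.

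The top of the uncorrected either-visit range needs correlations as low as 0.5. With 0.8 between visits and 0.9 between outcomes it is 13.3%, and with 0.9 and 0.95 it is 11.7%.

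**Split results.** At the strongest correlation in the second model, month 6, uncorrected: A alone is significant in 5.06% of null trials, B in 4.69%, either in 7.91%. Both are significant in 5.06 + 4.69 − 7.91 = 1.84%. Exactly one is significant in 7.91 − 1.84 = 6.07%, which is 6.07/7.91 = 77% of all trials with a significant result. In the healing-time model (month 6, percent reduction) the share is 62–70%. Splits are thus the usual form of a chance finding.

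**After the fix.** One named test has the level of that test, nominally 5%. If B is tested first and A only after success on B, the claim cannot be made without B, so the rate stays at B's level. Holm on A and B starts at 2.5% each: 1 − 0.975² = 4.94% if independent, and at most 2 × 2.5% = 5% at any correlation.

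**The case against.** The strongest reply is that the plan is silent, not permissive. It gives no threshold and nowhere says that any one significant test suffices. A reader might infer such a rule, but the text does not contain it, so the figures above are conditional on that reading. This stands. What also stands is that nothing excludes the reading.

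Second, the excess can be small. At one visit with Fisher's test it is nil to about 1 percentage point over 5%, and at month 6 with nearly all ulcers closed there is none even with uncorrected chi-square. A reader might therefore infer too much from any statement that the rate always exceeds 5%. It is only right to say that it can. However, the plan names chi-square and gives no expected healing rate, so the favourable case cannot be relied on.

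Third, "comparison of means, generalized linear model" might be taken as two rival methods for A. It can equally mean that the means are compared through a generalized linear model. The concern does not need a second method, and none is counted above.

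Fourth, part of the inflation comes from the open visit, which needs repair in its own right. That is fair. With the visit fixed, A and B still compete for one claim, at the smaller one-visit rates.

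Last, a 30-patient single-centre study might be excused as exploratory. The documents do not call it that; they describe a randomized trial meant to establish whether one treatment is better.

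**Conclusion.** The concern holds in qualified form. The plan leaves the error rate of its one effectiveness claim uncontrolled and gives no conclusion for a split result. At an assumed two-sided 5% per test and 15 per arm, the rate could reach about 9% at a single visit and about 13% if either visit may be used, both with uncorrected chi-square. With Fisher's test the corresponding upper values are about 6% and 8%. All of this assumes that a significant result on either outcome is taken as sufficient.

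Two larger figures are tempting but unsupported. Four independent tests would give 1 − 0.95⁴ = 18.5%, but closure and area reduction are measured on the same single ulcer and are not independent, and the plan does not say that tests will be run at both visits. Adding VEINES-QOL/Sym and VCSS at both visits would give 19–34% over eight tests, but the analysis paragraph names no test for them, and they serve separate aims.

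This should be corrected. It does not invalidate the design, and it cannot be credibly repaired once results have been seen.

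**What to change.** In the analysis paragraph, before enrolment:

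- Name one primary outcome, at one named visit, by one method, at two-sided 5%. Proportion of ulcers closed is a workable example. If it is chosen, state whether the test is uncorrected chi-square, continuity-corrected or Fisher's.
- State the visit explicitly, with the comparison it represents: before ablation in arm 2 at month 3, after it at month 6. The sponsor must choose which question is primary.
- Test healing rate by the generalized linear model only if the primary is significant. If A and B are to have equal standing, apply Holm to the pair at the named visit: smaller p-value against 2.5%, then the other against 5%.
- Report the other visit, VEINES-QOL/Sym and VCSS as secondary, with 95% confidence intervals. They cannot on their own support the claim that one arm is better.

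The cost is a few sentences, with no added patients or data. A significant secondary result can no longer carry the claim. Holm costs some power. For an assumed 0.8 SD difference in A with 15 per arm, the standardized effect is 0.8/√(2/15) = 2.19. Normal-approximation power is Φ(2.19 − 1.96) = 59% at 5% and Φ(2.19 − 2.24) = 48% at 2.5%. The loss for A is therefore at most about 11 points, and there is none when B passes at 2.5%. Ordered testing has no such cost for the primary.

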Another popular form of treatment is sclerotherapy. Either a foam mixture or a solution is injected into the effected veins causing inflammation and scarring. Over time this leads to destruction of the veins. This treatment is also commonly used with compression therapy. This technique promotes rapid healing usually occurring within 4 to 8 weeks after the initial treatment and long term recurrence rates⁹. This route is much less invasive, quicker, and less painful than the historical procedure of vein stripping.

Although there have been several studies performed on the significance of endovenous ablation and sclerotherapy, there is very little data or evidence to support the effectiveness of endovenous ablation in addition to sclerotherapy and compression in the treatment of venous ulcers and their reoccurrence. There is also very little data on whether receiving sclerotherapy and ablation together at the start of treatment, has any benefit over receiving sclerotherapy at the start of treatment and conducting ablation at a later time.

Research Question

Do outcomes of sclerotherapy of the ulcer bed alone, differ from a combination of ablation and injections?

Specific Aims

Our specific aims for this study are as follows:

Efficacy:

1. To determine if receiving sclerotherapy and ablation along with compression therapy at the start of treatment (arm 1) has any benefit over receiving sclerotherapy at the start of treatment and ablation 3 months later along with compression therapy (arm 2) in the treatment of chronic venous ulcers.
2. To compare and determine which arm has improved scores for quality of life (using the VEINES-QOL/Sym questionnaire).
3. To compare and determine which arm has improved venous clinical severity scores (VCSS).
4. To determine ulcer outcome and need for retreatment in arm 1 versus arm 2.

Safety:

1. To determine which arm puts patients at greater risk of increased healing times in the treatment of chronic venous ulcers.

Methods

Patients who are treated at Jobst Vascular Institute (JVI) will be evaluated for potential enrollment in this prospective study. Those who qualify, or their legally authorized representative (LAR), will be approached with study information and informed consent. Patients, or their LAR, who agree to participate will be consented and enrolled in the study.

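### The analysis names neither a primary visit nor a primary outcome, although the 3- and 6-month contrasts answer different questions; secondarily, no baseline ulcer-size covariate is named

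*Combined protocol and SAP*

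**What the plan says.** All places are in the combined protocol and SAP.

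- **Visits (Methods).** Ulcer size and healing rate are assessed at 3 months, and at that appointment: "All patients in arm 2, will receive ablation at this time". They are assessed again later: "Six months following initial treatment, the patients will return for another follow up visit where ulcer size, symptoms, healing rate, quality of life".
- **Questions.** The Research Question asks: "Do outcomes of sclerotherapy of the ulcer bed alone, differ from a combination of ablation and injections". Aim 1 under Specific Aims instead compares ablation at the start with ablation three months later.
- **Analysis (last paragraph of Methods).** The whole analysis is one sentence on group differences in "ulcer healing rate (comparison of means, generalized linear model), and B. proportion of healed ulcers (Chi square". It gives no visit, no primary outcome, no covariate, no definition of healing rate and no significance level.
- **Population and allocation.** The inclusion criterion is "Patients who have saphenous vein reflux and a single venous ulcer of any size". Allocation uses "30 opaque envelopes, 15 indicating arm 1 and 15 indicating arm 2", and no stratification by size is described. Number of Subjects sets a goal of 15 per arm and a maximum of 40 in total.
- **Before treatment (Methods).** Patients fill in VEINES-QOL/Sym and "complete the venous clinical severity score (VCSS) questionnaire prior to treatment". Ulcer size is not listed there. The variables sheet that Methods refers to is not among the supplied documents.

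**The concern.** Because arm 2 is ablated at 3 months, the two visits compare different treatments. A p-value for healing rate cannot be interpreted until the visit is known. If the visit and the primary outcome are settled only after the data are in, the more favourable result can be reported, and the nominal 5% error rate no longer applies.

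The second strand is precision. With no size limit at entry and 15 per arm, starting sizes may differ noticeably between arms by chance. If starting size predicts healing, an analysis that ignores it has a wider interval than it needs. In a trial with such an imbalance, the estimate is also shifted.

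**Working it through.** The plan states no power, effect size, SD or healing proportion, so there is no figure of its own to reproduce. I assume a two-sided 5% level. The correlation r between starting size and healing is also assumed, at 0.3, 0.5 and 0.7.

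**1. What each visit compares.** At 3 months, before the arm 2 ablation, arm 1 has had sclerotherapy and ablation and arm 2 sclerotherapy only; this matches the Research Question. At 6 months both arms have had both treatments and differ only in when ablation was done; this matches aim 1.

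**2. Leaving the visit open.** If the two visits' tests were independent, the chance that at least one is falsely significant would be 1 − 0.95² = 9.75%. Simulation with no true effect (15 per arm, no ceiling, size-adjusted test, visits correlated 0.5 to 0.9, r from 0.3 to 0.7; 60,000 trials) gives 7.4–9.8%. The position in that range depends on the correlation v between visits after removing size, (v − r²)/(1 − r²):
- v = 0.5, r = 0.7: (0.5 − 0.49)/0.51 = 0.02. The visits are nearly independent, which is extreme for the same ulcer; this gives the 10% end.
- v = 0.9, r = 0.3: (0.9 − 0.09)/0.91 = 0.89. This gives about 7%.

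Choosing between adjusted and unadjusted tests at one visit gives 6–8%.

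**3. Leaving the outcome open.** At a single visit with no true effect, 15 per arm and 35–80% healed, a size-adjusted rank test of healing rate or the chi-square (either one) is significant in about 6–9% of trials.

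**4. Chance imbalance in size.** The standardised difference in mean starting size has SD √(2/n).
- n = 15: √(2/15) = 0.365, so P(|difference| > 0.5 SD) = 2[1 − Φ(0.5/0.365)] = 17%.
- n = 20 (the maximum, if all are analysed): √(2/20) = 0.316, giving 11%.

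An imbalance of 0.5 SD shifts the unadjusted difference by 0.5r, that is 0.15, 0.25 or 0.35 SD.

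**5. Precision.** The ratio of adjusted to unadjusted standard error is √(1 − r²) × √(1 + 1/(2n − 4)). At n = 15 the second factor is √(27/26) = 1.019, so the ratio is 1.02, 0.97, 0.88 and 0.73 at r = 0, 0.3, 0.5 and 0.7. It equals 1 when r² = 1/27, or r = 0.19; below that, adjustment gains nothing.

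**6. Power for an assumed 0.8 SD effect, 15 per arm** (simulation). The ceiling rows cap percent reduction at 100% and analyse ranks.

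| Situation | Unadjusted | Adjusted, r = 0 | 0.3 | 0.5 | 0.7 |
|---|---|---|---|---|---|
| No ceiling | 56% | 55% | 58–59% | 67% | 83% |
| 50% of controls healed, 79% treated | 41% | 40% | 42% | 47% | 55% |
| 80% of controls healed, 95% treated | 18–19% | 19% | 19–20% | 21% | 23% |

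The gains at r = 0.3/0.5/0.7 are about 2–3/11/27, 1/5/13 and 1/2/4 points. Without a ceiling, the false-positive rates of the unadjusted and adjusted tests are both 4.9–5.2%.

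**7. Proportion healed.** For 50% against 79%, chi-square has 38–40% power and a Firth logistic model with log size 37/40/48%. For 80% against 95% the figures are 19% and 17/17/18%.

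**8. Why the definition belongs in the fix.** Take two hypothetical circular ulcers whose edges advance 0.05 cm a week for 12 weeks (0.6 cm). The radius of a 2 cm² ulcer falls from 0.80 to 0.20 cm: 0.16 cm² a week, 94% reduction. That of a 40 cm² ulcer falls from 3.57 to 2.97 cm: 1.03 cm² a week, 31% reduction. Absolute and percent rates rank the same healing in opposite order.

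**The case against.** Randomisation makes each unadjusted test valid, and the generalized linear model already named could carry starting size. The documents give no correlation between size and healing, so the gain is hypothetical, and it is small if most ulcers close. The absent variables sheet may define healing rate and list pre-treatment area. Percent reduction is only one option: patients are seen weekly and the safety aim concerns healing time, so time to healing could be used.

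Most of this stands. It makes size adjustment a secondary recommendation, and the definition below an example. It does not answer the open visit and outcome, which need no assumption about size.

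A reader might infer more than the documents support:
- *That admitting any size biases the comparison or invalidates the test.* Under randomised allocation it does neither. The loss is precision, plus a shift in those trials that happen to be imbalanced.
- *That the plan rules out adjustment.* It names no covariate but names a model that could hold one. The wording in brackets may also describe one method rather than two.
- *That chi-square is a defect because it cannot carry size.* Step 7 shows no gain from the Firth model except at r = 0.7 with half of controls healed.
- *That the error rate is known to be 10% or more.* The upper figure is an extreme case, and the plan does not say that the better visit would be chosen; it leaves that open.

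**Conclusion.** The point holds, led by the visit. The supplied text does not say which of two different treatment contrasts is tested, or which of the two outcomes decides. The consequence is about 7–10% false positives if the better visit is reported, and about 6–9% if the better outcome is. Both ranges rest on assumed correlations or healed fractions, and the visit figures also assume no ceiling.

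The size covariate is secondary and conditional. Its benefit runs from a loss of 1–2 points of power to a gain of about 27, depending on r and on how many ulcers heal. The Background points both ways on healing: over half of venous ulcers are said to be unhealed after 9 months, yet of sclerotherapy it says "This technique promotes rapid healing usually occurring within 4 to 8 weeks after the initial treatment". A gain near the top of the range should therefore not be presumed. Confidence is medium, because the variables sheet has not been seen.

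**What to change.** In the analysis paragraph of Methods, before any data are seen:

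1. Name one primary visit to match the question the sponsor holds to be main: 3 months, measured before the arm 2 ablation, for the Research Question; or 6 months for aim 1. Make the other visit secondary.
2. Name one primary outcome and one test. For example: percent reduction in ulcer area from the pre-treatment measurement, with a healed ulcer counted as 100%, in the planned model with arm and log pre-treatment area, using ranks if many ulcers are expected to heal.
3. Make the chi-square on proportion healed at the same visit secondary, and drop the separate unadjusted comparison of means as a reported test.
4. Confirm that pre-treatment ulcer area is recorded. It cannot be recovered once treatment has begun.
5. For aims 2 and 3, compare VEINES-QOL/Sym and VCSS by ANCOVA on the pre-treatment values already collected.

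The cost is analysis wording, one degree of freedom, 1–2 points of power if size is unrelated to healing, and one measurement if area is not already on the sheet. If ranks are used, any adjusted mean difference should be labelled descriptive: in simulation its nominal 95% interval covered about 94% with half of controls healed and 84% with 80% healed.
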